### 1.1 Background

#### 1.1.1 Study design

This is a prospective, randomized, evaluator-blinded, no-treatment controlled, parallel group, multicenter US study to evaluate the effectiveness and safety of Restylane-L for correction of Infraorbital Hollows (IOH). Eligible subjects randomized to receive treatment will be injected by the Treating Investigator at Day 1. Optional touch-up treatment may be administered after 1 month of initial treatment, if deemed necessary by Treating Investigator and subject to obtain optimal aesthetic improvement. Optimal aesthetic improvement is defined as at least 1 grade improvement, from baseline, on the GIHS and best correction that can be achieved as agreed by the Treating Investigator and the subject.

At the month 12 visit, the no-treatment comparator subjects will be offered an optional Restylane-L treatment. The subjects who received Restylane-L at the baseline visit will also be offered an optional additional treatment if optimal aesthetic improvement is not maintained (as determined by the Treating Investigator and subject). For subjects receiving optional treatment at month 12 the effectiveness and safety data will be collected for another 6 months. A subject will be involved in the study for up to 19 months including 30 days screening and 6 months follow-up after optional treatment at month 12. The study flow chart is provided in Appendix A.

#### 1.1.2 Number of subjects and randomization

Approximately 329 subjects will be included (CC) to treatment with Restylane-L or no treatment. In the treatment group approximately 146 subjects will get injections using needle and approximately 136 subjects using cannula. At least 36 subjects will be Fitzpatrick skin type (FST) IV - VI, with at least 18 of those subjects with FST V - VI. Approximately 47 subjects will be randomized to notreatment at baseline.

The randomization list will be stratified by FST group (I-III, IV, and V-VI). The FST I-III group will be further stratified by study site. The FST IV and FST V-VI groups will be further stratified at needle or cannula level (needle sites pooled into a needle stratum, and cannula sites pooled into a cannula stratum). Approximately half of the sites will be using needle and the other half will be using cannula for injection.

The Treating Investigator and subjects will not be blinded to study treatments.

	Title 43USTT1904 Statistical analysis plan - Tear Trough	Doc id
GALDERMA 657, 1981		MA-42205

2022-08-17 17:26

#### 1.2 Study objectives

#### 1.2.1 Primary effectiveness objective

The primary objective of the study is to evaluate the effectiveness of Restylane-L (injected using needle or cannula) versus no-treatment control in the correction of Infraorbital Hollows using a Blinded Evaluator's assessment of the Galderma Infraorbital Hollows Scale (GIHS).

#### 1.2.2 Secondary effectiveness objectives

The secondary objectives are to evaluate the effectiveness of Restylane-L (injected using needle or cannula) versus no-treatment control in the correction of Infraorbital Hollows using the following:

- Blinded Evaluator assessment of the GIHS
- Global Aesthetic Improvement Scale (GAIS)

#### 1.2.3 Safety objectives

The safety objectives are to evaluate AEs and pre-defined, expected post-treatment events reported during the first 28 days after treatment.

#### 1.3 Effectiveness assessments

For all assessments, baseline will be defined as the observation that is closest to, but prior to, the study injection on Day 1.

CCI

[figure not shown]
#### 1.3.1 Galderma Infraorbital Hollows Scale (GIHS)

The GIHS is a four-point scale for assessment of Infraorbital Hollows (Appendix B). Each score in the GIHS is exemplified by Photographic images of the scale. The Blinded Evaluator and Treating Investigator will perform live assessment of the subject's right and left Infraorbital Hollow separately.

The Blinded Evaluator will perform GIHS at:

- Screening/Baseline visit(s)
- Months 3, 6, 9, and 12 after randomization
- Months 3 and 6 after optional treatment. For assessments at these two visits specifically, the
  evaluator will be considered unblinded as these assessments are performed on all subjects
  that elect to receive the optional treatment.

A responder indicator will be created to identify subjects that had at least one-point improvement from baseline, on both sides of the face concurrently. If at any given post-baseline visit, both left side of face GIHS change from baseline score and right side of face GIHS change from baseline score are at least 1, the subject will be considered a responder for that visit.

2022-08-17 17:26

GIHS change from baseline will be calculated following the formula described above (Section 1.3).

The Treating Investigator will perform GIHS during the following visits:

- Screening/Baseline visit(s)
- Month 1 and 12 after randomization.

The Treating Investigator will only perform the GIHS assessment for the purpose of assessing treatment eligibility. These assessments are not included in any analyses.

#### Global Aesthetic Improvement Scale (GAIS) 1.3.2

The GAIS is used to assess the aesthetic improvement of the Infraorbital Hollows. It consists of one question, "How would you describe the aesthetic improvement of your tear troughs today compare to the photograph taken before treatment?" rated on a seven-point scale (Appendix C GAIS). Responses can range from 'Very Much Improved' to 'Very Much Worse.'

Both the Treating Investigator and the subject will complete the GAIS, independently, rating their assessment for aesthetic change by comparing the appearance at follow-up visits to baseline photographs (obtained prior to injection at baseline). The Treating Investigator and the subject will complete the GAIS independently. The GAIS will be assessed at:

- Month 1, 3, 6, 9, and 12 after randomization
- Month 1 after optional touch-up
- Month 1, 3, and 6 after optional treatment.

A responder indicator will be created to identify subjects that experienced an improvement in aesthetic appearance of their infraorbital hollows as assessed by the Treating Investigator. If at any given visit the Treating Investigator selects 'Improved,' 'Much Improved,' or 'Very Much Improved' on the GAIS, the subject will be considered a Responder at that visit. A similar responder variable will be created for the GAIS assessed by the subject.

Effective date: 2021-12-17 13:25

TEIN 43USTT1904 Statistical analysis plan - Tear Trough

Doc id

Print date:

MA-42205

2022-08-17 17:26

CCI			

2022-08-17 17:26

#### 1.4 Effectiveness endpoints

#### 1.4.1 Primary effectiveness endpoint/estimand

The primary endpoint of the study is the Responder rate based on the Blinded Evaluators' live assessment of the GIHS at 3 months after baseline.

A responder is defined as a subject with at least one-point improvement from baseline, on both sides of the face concurrently.

The primary estimand is then the difference in proportions of GIHS responders at Month 3 in the Restylane-L group versus a No Treatment control group in subjects who are randomized at baseline and did not have a remote month 3 GIHS assessment.

#### 1.4.2 Secondary effectiveness endpoints/estimands

Secondary effectiveness endpoints include:

#### (i) Blinded Evaluator Assessment of GIHS

Responder rate based on the Blinded Evaluators' live assessment of the GIHS, at 6, 9, and 12 months after baseline and at 3 and 6 months after optional treatment.

A responder is defined as a subject with at least one-point improvement from baseline, on both sides of the face concurrently, at each of the timepoints separately.

The estimand is then the difference in proportions of GIHS responders at Months 6, 9, and 12 (before treatment) after baseline and the proportions of GIHS responders at Months 3 and 6 after optional treatment in the Restylane-L group versus a No Treatment control group in subjects who are randomized at baseline.

#### (ii) GAIS

Number and proportion of subjects having at least "Improved" on the GAIS, as assessed live by the Subject and Treating Investigator separately at all follow-up visits after baseline.

The estimand is the proportions of GAIS responders, assessed separately by Treating Investigator and subject, at each follow-up visit up until Month 12 (before treatment), and the proportions of GAIS responders at Months 3 and 6 after optional treatment in the Restylane-L group versus a No Treatment control group in subjects who are randomized at baseline.

GALDERMA

Title
43USTT1904 Statistical analysis plan - Tear Trough

MA-42205

Print date:

2022-08-17 17:26

#### 1.5 Safety assessments

For details regarding the safety assessments, please refer to the Clinical Study Protocol (CSP) Section 8.

#### 1.5.1 Adverse events

[figure not shown]
Adverse events (AEs) are to be monitored throughout the course of the study. All AEs reported will be coded using the Medical Dictionary for Regulatory Activities (MedDRA, version in force at the time of database freeze) and classified by MedDRA preferred term (PT) and system organ class (SOC).

A two-point scale ("Yes" or "No" response) will be used for the causality assessments. The Treating Investigator should be asked to indicate a response to each of the following questions in the eCRF:

- "Do you consider that there is a reasonable possibility that the event may have been caused by the study product?"
- "Do you consider that there is a reasonable possibility that the event may have been caused by the study product injection procedure?"

If any of these questions is answered with a 'Yes,' the AE will be considered related. These assessments will also be reviewed by the Sponsor.

#### Adverse Events of Special Interest (AESI)

2022-08-17 17:26

Due to the injection location of this study, AESIs will be considered and collected. All incidences of visual disturbances, regardless of relationship to study product or seriousness, will be considered as a potential AESI. These include, but are not limited to, the following: Any change in vision, any loss of vision, blurry vision, double vision, pain in or around the eye, blind spot or shadow in the visual field, trouble moving eyes, any change in Snellen visual acuity including change of one line or greater.

#### 1.5.2 Vision Function Assessment

Vision function assessments include Snellen visual acuity test, extraocular muscle function test, and confrontation visual field. Vision function assessments will be performed both before and 30 minutes after any study injection.

#### 1.5.3 Subject Study Diary

Subjects will complete a 28-day symptom diary, starting on the day of injection, for each treatment (initial, optional touch-up, optional re-treatment).

#### 1.5.4 Laboratory assessments

For all women of childbearing potential, a urine pregnancy test is required prior to receiving any study injections.

#### 1.6 Safety endpoints/estimands

The Safety endpoints/estimands for this study include:

- (vii) Incidence and intensity of all AEs collected during the whole study
- (viii) Incidence, intensity, and duration (number of hours) of pre-defined, expected posttreatment events collected using a subject diary for 28 days after treatment

	Title 43USTT1904 Statistical analysis plan - Tear Trough	Doc id
GALDERMA		MA-42205

2022-08-17 17:26

In general, all analyses will be summarized by injection tool and treatment group (Restylane-L Needle, Restylane-L Cannula, Restylane-L (pooled), No Treatment), unless otherwise stated in Section 2.4 or Section 2.5.

#### 2.1.1 Visit Windows

Study visits are expected to occur according to the protocol schedule in Appendix G. All data will be tabulated per the evaluation visit as recorded on the eCRF even if the assessment is outside of the visit window. In data listings, the relative study day (in relation to randomization date) of all dates will be presented. There will not be any windowing for unscheduled visits in the analysis, and unscheduled visits will not be included in any analyses. Unscheduled visits, if any, will be presented in listings only.

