Although most AEs occur within days to weeks following the implant procedure, some AEs such as swelling and serious infections/abscess have been reported several weeks to months after the injection. Vascular occlusion resulting in ischemia/necrosis and visual disturbances including blindness have been reported following injection of any soft tissue filler in the face especially in the nose, glabella, periorbital areas, nasolabial folds and cheek, with a time to onset ranging from immediate to a few weeks following injection. Vascular compromise may occur due to an inadvertent intravascular injection or as a result of vascular compression associated with implantation of any injectable product. This may manifest as blanching, discoloration, necrosis or ulceration at the implant site or in the area supplied by the blood vessels affected; or rarely as ischemic events in other organs due to embolisation. Isolated rare cases of ischemic events affecting the eye (leading to visual loss) and the brain (resulting in cerebral infarction) following facial aesthetic treatments have been reported. Reported treatments included anticoagulant, epinephrine, aspirin, hyaluronidase, steroid treatment, analgesics, antibiotics, local wound care, drainage, surgery and hyperbaric oxygen. Outcome of the events ranged from resolved to ongoing at the time of last contact. In many of the events requiring medical intervention, the patient was injected into the highly vascularized areas of the glabella, nose, and periorbital area.

According to published literature AEs are mostly described as injection site reactions minor such as including some degree of bruising, erythema, local swelling, contour irregularity, and color change.

Post-market surveillance reporting with device location defined as *Tear trough* alone or in combination with other locations (cheek, glabella, nasolabial folds, jaw lines, temple, eye lid,

	Title 43USTT1904 CSP Infraorbital Hollows	Doc id MA-40833
--	---	---------------------------

or oral commission) are generally in line with the overall reporting pattern for *Restylane*. To date, no unacceptable risks have been identified for *Restylane-L* treatment. Any potential concerns related to the clinical study have been assessed and the remaining risks are disclosed in the study specific IFU.

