- Interview subject regarding any AEs that have occurred since receiving treatment. If AEs are reported, notify the Investigator immediately and determine whether subject should return to the site for an unscheduled visit. The Investigator should assess all reported AEs in a timely manner.
- Interview subject regarding the Diary completion and reported events since receiving treatment. Remind subject to complete the Diary daily and bring it to the next on-site visit.
- Remind subject of the next scheduled on-site visit.

	Title 43USTT1904 CSP Infraorbital Hollows	Doc id MA-40833
--	---	---------------------------

Effective date: 2021-12-15 20:29

4.7.4 Visit 3: Follow up visit 14 days (\pm 3 days) after Baseline/Day 1

- Interview subject regarding any concomitant therapies and record subject's weight.
- Interview subject and evaluate any AEs, and post-treatment AEs by Treating Investigator (if randomized to treatment) that have occurred since the last visit.
- Obtain photographs.
- Perform Vision Function Assessments.
- Interview subject regarding the Diary completion and reported events since receiving treatment. Remind subject to complete the Diary daily and bring it to the next on-site visit.
- Remind subject of the next scheduled on-site visit.

4.7.5 Visit 4: Follow-up visit 1 month (+ 7 days) after Baseline/Day 1/ Optional touch-up

- Interview the subject regarding concomitant therapies and record subject's weight.
- Interview subject and evaluate any AEs, and post-treatment AEs by Treating Investigator (if randomized to treatment) that have occurred since the last visit.
- Obtain photographs (if treatment is given, ensure photos are taken prior to injection)
- Assessments to be performed, prior to optional touch-up:
 - GIHS – Treating Investigator
 - GAIS – Treating Investigator and Subject

CCI

- Schedule Visit 5, 3 months (\pm 7 days) after the Baseline visit (Visit 1b).

For subjects randomized to treatment

- Collect and review Subject Diary for subjects randomized to treatment:
 - Review diary entries for completeness and legibility.
 - If the subject handwrites entries on the diary pages, review these entries with the subject and clarify as needed. Record all clarifications on the subject's source documents and record the Diary data into the eCRF.

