#### 2.5.4 Vision Function Assessment

[figure not shown]
For the extraocular muscle function test and confrontation visual field vision function assessments (specified in Section 1.5.2) the number and percentage of subjects reporting normal and abnormal test results will be presented by treatment group and by visit.

For Snellen visual acuity test, subjects that experience a worsening of 1+ line change in at least one eye during the course of the study will be summarized by eye, treatment group, and visit. Only subjects that experience a worsening line change will be considered in the analysis; the number and percentage of subjects that experience a worsening of 1+ line change in at least one eye during the course of the study will be presented. The number of subjects with a non-missing Snellen assessment at a respective visit will be used as the denominator.

A 1+ worsening line change in Snellen visual acuity is when a subject moves up at least one line of letters on the Snellen Eye Chart (Figure 1). For example, if a subject's visual acuity at baseline is 20/40 for the left and right eyes and then at Visit 3 is 20/70 for the left eye and 20/50 in the right eye, the subject experienced a 2-line worsening for the left eye and a 1-line worsening in the right eye.

Figure 1. Snellen Eye Chart

2022-08-17 17:26

The visual function assessment data will also be presented by treatment and subject in data listing. This listing will only include subjects with a change in visual function as determined by any of the three vision assessments.

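### The vision-function tables in SAP 2.5.4 omit any change recorded only at an unscheduled visit, so they cannot give the study-wide count their text promises

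*SAP*

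**What the plan says.** **The exclusion.** SAP 2.1.1 (Visit Windows), under General methods, says that "unscheduled visits will not be included in any analyses. Unscheduled visits, if any, will be presented in listings only". Neither 2.1.1 nor 2.5.4 sets it aside for vision data in the published text.

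**The vision tables.** SAP 2.5.4 counts subjects with a "worsening of 1+ line change in at least one eye during the course of the study", but lays the result out by visit: worsening "during the course of the study will be summarized by eye, treatment group, and visit". The denominator is also tied to the visit: "The number of subjects with a non-missing Snellen assessment at a respective visit will be used as the denominator". For the other two tests, "the number and percentage of subjects reporting normal and abnormal test results will be presented by treatment group and by visit". On the listing, 2.5.4 says: "This listing will only include subjects with a change in visual function as determined by any of the three vision assessments".

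**Where unscheduled visits come from.** At the 72-hour call after baseline treatment (Protocol 4.7.3), staff who hear of an AE must notify the Investigator and "determine whether subject should return to the site for an unscheduled visit". The calls after touch-up (4.7.6) and after optional treatment (4.7.11) carry the same instruction.

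**The risk.** Protocol 2.4 describes vascular occlusion and visual disturbance, including blindness, "with a time to onset ranging from immediate to a few weeks following injection".

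**The concern.** Visual disturbance is the adverse event of special interest for this injection site. The vision tests are the objective record of it. A subject seen between planned visits because of a complaint is more likely than most to have an abnormal test, and that visit is the kind SAP 2.1.1 removes.

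Suppose a two-line acuity loss is recorded at an unscheduled visit on Day 5 and has resolved by the 14-day visit. The Snellen table shows that subject as not worsened, although its text speaks of the whole study. If the loss was reported as an AESI, the clinical study report would show a visual event in one table and no worsening in another. A reader comparing needle, cannula and no treatment would have no objective rate that includes such cases.

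**Working it through.** No sample-size, power or error-rate figure is at issue. The check sets the rules side by side and adds two short calculations.

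**1. Rule against table.** The text of 2.5.4 needs every post-baseline test. Its layout and denominator need a visit. Rule 2.1.1 allows only scheduled visits. A subject whose only worsening was recorded at an unscheduled visit meets the wording but has no cell in the table.

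**2. Where such a change would appear.**

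| Change recorded only at an unscheduled visit | SAP 2.5.4 table | Listing | AE/AESI tables (SAP 2.5.2) |
|---|---|---|---|
| Snellen, one line or more | No | Yes | Yes, if reported as Protocol 8.2.1 requires |
| Eye movement | No | Yes | If a visual disturbance is reported (8.1.1), or the Investigator judges the finding an AE (8.2.2) |
| Visual field | No | Yes | Same two conditions (8.1.1, 8.2.3) |

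Protocol 8.2.1 sends a Snellen line change to the Sponsor as an AESI and has it assessed as an AE. Sections 8.2.2 and 8.2.3 ask only that a change be assessed as a potential AE. An isolated eye-movement or field finding judged not to be an AE could therefore reach no summary table.

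The AESI row is not a substitute for the vision tables. It pools eye pain, blurred vision and acuity change. Protocol 8.1.1 also gives no direction for an acuity change, whereas SAP 2.5.4 counts worsening only.

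**3. How much of the year has a scheduled test.** Inputs: Protocol Table 1 with its footnotes, and a month of 28 days (Protocol 4.3). Month 12 is day 12 × 28 = 336. No vision test is scheduled at Months 3, 6 or 9. The Month 12 test is omitted if no treatment is given then.

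- *No touch-up.* The scheduled post-injection tests are at 30 minutes and at Day 14 ± 3. Days from the last of these to Month 12: 336 − 14 = 322 (322/336 = 95.8%). At the window limits: (336 − 7) − (14 + 3) = 312 (92.9%).
- *With touch-up.* The last scheduled test before Month 12 is 14 days after the touch-up, nominally day 28 + 14 = 42. Gap: 336 − 42 = 294 (87.5%). At the window limits: (336 − 7) − (28 + 7 + 14 + 3) = 277 (82.4%).
- *Controls.* After screening or baseline, no vision test is scheduled unless the subject takes the Month 12 treatment.

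Scheduled testing therefore leaves 82% to 96% of the first 12 months without a planned test.

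**4. Size.** The documents give no expected number of changes seen only at unscheduled visits, so these counts are assumptions. The planned treated group is 146 + 136 = 282 (SAP 2.7).

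| Assumed subjects | Of 282 treated | If all needle (146) | If all cannula (136) |
|---|---|---|---|
| 1 | 0.35% | 0.68% | 0.74% |
| 3 | 1.06% | 2.05% | 2.21% |
| 5 | 1.77% | 3.42% | 3.68% |

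**The case against.** The strongest reply is that vision loss is counted as an event, whatever visit it was found at. Protocol 8.1.1 makes every visual disturbance an AESI regardless of relationship or seriousness. Protocol 8.5.5 extends AE reporting to extra visits between planned ones. SAP 2.5.2 assigns AEs to treatment periods by onset date and has rows for any AESI and any serious AESI. The stopping rule in Protocol 8.5.8 runs on SAE reports. All of this stands. A reader might infer from SAP 2.1.1 that the trial under-counts vision loss, and the documents do not support that.

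A reader might also infer that every symptom-driven vision test after about Day 17 is lost. That goes too far. SAP 2.1.1 excludes unscheduled visits and otherwise tabulates data under the visit recorded on the eCRF, so an extra test recorded at a scheduled visit is not removed. Nor does either document require a vision test at an unscheduled visit. For changes in vision, the diary directs the subject to an eye doctor (Protocol 8.3), and that examination may reach the database only through AE reporting.

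Three further points are fair. The vision tables are not a named safety endpoint (SAP 1.6, Protocol 3.1.3), and the safety analysis is descriptive. Changes remain visible in the listing. A percentage calculated among subjects who attended an unscheduled visit would be self-selected and hard to interpret, so keeping the by-visit rows on scheduled visits is sound.

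None of this repairs the mismatch between the stated count and the tests allowed into it. A listing gives no rate by group, and the AE route leaves eye-movement and field findings partly to judgement.

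**Conclusion.** The point holds as a completeness defect in the SAP 2.5.4 tables. Followed as written, the plan cannot deliver its count of subjects who worsen during the study, and those tables may disagree with the AESI tables. No hypothesis test or named endpoint is affected. Reported visual loss remains counted in the AE and AESI summaries.

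This rests on two assumptions: that some vision tests are recorded under unscheduled visits, and that 2.1.1 is applied literally to safety data. The number of subjects affected is unknown, could be zero and is probably small. Severity is minor to moderate.

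**What to change.** 1. In SAP 2.1.1, limit the exclusion of unscheduled visits to by-visit summaries, and state that AE and AESI summaries are unaffected.
2. In SAP 2.5.4, add for each treatment period and treatment group a row for the worst value at any time after injection, for Snellen acuity, extraocular muscle function and visual field. Use scheduled and unscheduled tests. The denominator is the number of subjects with any post-injection test in that period. Name the reference test for the Snellen line change.
3. Keep the existing by-visit rows on scheduled visits.

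Controls have no injection before Month 12 and no scheduled test after screening or baseline. The new row therefore describes treated periods and should not be read as a randomized comparison.

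The cost is a few sentences and minor programming, with no new data collection. The reported rate of vision change may rise slightly.
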